## PROTOCOL AMENDMENT SUMMARY OF CHANGES TABLE

Document History		
Document	Date	Type of amendment
Original Protocol	11 Dec 2023	Not applicable

This document cannot be used to support any marketing application and any extensions or variations thereof.  
PUBLIC COPY

## 1 PROTOCOL SUMMARY

### 1.1 Synopsis

**Protocol title:**

An open-label, single center, randomized, 2-way crossover, single dose, bioequivalence study of zilucoplan injected subcutaneously either by a prefilled syringe or an auto-injector in healthy adult participants

**Short title:**

An open-label, single center, randomized, 2-way crossover, single dose, bioequivalence study of zilucoplan injected subcutaneously in healthy adult participants

**Rationale:**

Myasthenia gravis (MG) is a serious, sometimes life-threatening, debilitating condition associated with numerous symptoms, including muscular weakness and fatigue. Some patients can manage their symptoms with oral medications, such as oral acetylcholinesterase inhibitors, corticosteroids, or nonsteroidal immunosuppressants. In addition, intravenous (IV) immunoglobulin G and plasma exchange treatment can be utilized as well. For those whose symptoms are not well managed by these medications, a potential alternative is long term treatment with approved IV complement component 5 (C5) inhibitors (eg, eculizumab or ravulizumab) which have proven effective at treating MG symptoms.

Zilucoplan (RA101495; ZLP) has recently been approved in Japan, the US, and the EU. It reduces the administration burden, can be used by patients with difficult venous access, or who are in underserved or rural populations where economic access to IV infusions is prohibitive. Zilucoplan is currently approved as a pre-filled syringe (PFS) for subcutaneous (sc) injection; however, it is expected that there will be a need to have different treatment administration options available for the administration of ZLP and that individuals may prefer to have the option to administer their ZLP medication using an auto-injector (AI). DV0012 will, therefore, assess the bioequivalence of ZLP pharmacokinetics (PK) between a single sc injection of ZLP from a ZLP-PFS and ZLP-AI, and evaluate the ZLP PK, safety, and tolerability in healthy study participants who receive a single sc injection of ZLP from a ZLP-PFS and ZLP-AI.

## Objectives and endpoints

Objectives	Endpoints
Primary	

To establish the bioequivalence of ZLP pharmacokinetics (PK) after a single sc injection with ZLP safety syringe (ZLP-PFS) and ZLP-AI

	

Area under the plasma concentration-time curve from time 0 to infinity (AUC)

Area under the plasma concentration-time curve from time 0 to time t (AUC0-t)

Maximum observed plasma concentration (Cmax)

Secondary	

To evaluate the safety and tolerability of ZLP after a single sc injection with ZLP-PFS and ZLP-AI

	

Occurrence of treatment-emergent adverse events (TEAEs), serious adverse events (SAEs), and adverse device effects (ADEs, serious and nonserious) from Day 1 up to the End of Study (EOS) or Early Termination (ET) Visit

Exploratory	

To further evaluate the safety and tolerability of ZLP after a single sc injection with ZLP-PFS and ZLP-AI

To further evaluate the PK of ZLP after a single sc injection with ZLP-PFS and ZLP-AI

To evaluate device deficiencies

	

Change from Baseline in clinical laboratory tests (hematology, clinical chemistry, and urinalysis)

Terminal half-life (t1/2)

Apparent plasma clearance (CL/F)

Time to maximum observed concentration (tmax)

Apparent volume of distribution (Vz/F)

Device deficiencies as reported via the electronic case report form (eCRF)

## Overall design

DV0012 is a Phase 1, open-label, single-center, randomized, 2-way crossover study in 14 healthy study participants designed to establish bioequivalence in ZLP PK between a single sc injection of ZLP from a ZLP-PFS (reference) and a ZLP-AI (test), and to investigate the PK, safety, and tolerability in healthy study participants who receive a single sc injection of ZLP.

The crossover design allows each participant to receive a single ZLP injection with each of the 2 devices (ZLP-PFS and ZLP-AI). Zilucoplan will be administered as a single sc injection in the abdomen to evaluate the potential impact of using 2 different devices (ZLP-PFS and ZLP-AI) on the PK endpoints. The volume of ZLP will differ from participant to participant depending on their body weight on Treatment Period 1 Day -1.

Study personnel will administer 1 injection of ZLP to the study participant on Day 1 of each Treatment Period following detailed instructions that will have been provided. Injections into the abdomen must avoid the 5 cm/2-inch area around the belly button (navel). No injections should be administered into an area that is tender, red, bruised, hard, or that has scars or stretch marks.

Fourteen healthy study participants will be randomized 1:1 to treatment sequence AB or BA, where treatment A is ZLP-PFS injection device and treatment B is ZLP-AI injection device (see study schematic in Section 1.2). Following completion of the first Treatment Period and a 7-day Washout Period, study participants will then complete the second Treatment Period with the same dose level as in Treatment Period 1 but using the alternate device.

Study participants will have End of Study (EOS) procedures performed on the last sampling day (Day 35) of Treatment Period 2, in addition to the Day 35 procedures.

Study participants who are unable to complete the study will return to the study center for the Early Termination (ET) Visit as soon as possible after the time of withdrawal and will have all Day 35 and EOS procedures performed (ie, Day 35 of the Treatment Period in which they withdrew from the study).

### **Number of participants**

A sufficient number of study participants will be screened to ensure that 7 study participants are randomized to each of the 2 treatment sequences (14 study participants in total), with the objective of having at least 12 study participants complete the study. See Section 9.8 for more details. Study participants who withdraw or are withdrawn from the study after dosing will not be replaced. However, if the number of dropouts exceeds initial expectations, study participants who withdraw or are withdrawn might be replaced at the discretion of the Sponsor.

### **Treatment groups and duration**

[figure not shown]
Zilucoplan will be provided as a single-use injection in a needle safety device (ZLP-PFS) or a ZLP-AI device using weight-bracketed dosing (ie, participants will be provided ZLP-PFS or ZLP-AI containing fixed amounts of ZLP based on their weight, and each fixed amount will cover a range of participant weights).

The total maximum study duration per study participant will be up to 15 weeks, as follows:

- Screening Period: Up to 35 days (Days -35 to -2).
- In-Clinic Period (BL): 1 day (Day -1).
- Treatment Period 1 and Treatment Period 2: 5 weeks each (Days 1-35; approximately 5 times the half-life of ZLP). Each Treatment Period includes:
  - a 2-day In-Clinic Period (Days 1 and 2).
  - a 33-day Observation Period.
    - On Days 3, 5, 8, 15, 22, 29, and 35 of the Observation Period, participants will attend the study center to allow study assessments to be completed.
- Washout Period between Treatment Period 1 and Treatment Period 2: 1 week (7 days).
- The EOS Visit procedures will be performed on Day 35 of Treatment Period 2 (ie, on Study Day 77).

## 1.2 Schema

Figure 1-1: Study schematic

ZLP-AI=zilucoplan-autoinjector; ZLP-PFS=ZLP prefilled syringe

### 1.3 Schedule of Activities

**Table 1-1: Schedule of study assessments**

Procedure	Screening Period	In-Clinic Period (BL) c	Treatment Periods 1 and 2 d									EOS/ET e
			In-Clinic Period c		Observation Period c							
Day a	-35 to -2	-1	1	2	3	5	8	15	22	29	35	
Written informed consent	X											
Inclusion/exclusion criteria	X	X										
Demography	X											
Medical/surgical history	X											
Physical examination f	X	X									X	
Pregnancy test g	X	X										
Height and weight h	X	X										
Serum FSH level i	X											
Viral serology (HBsAg, HCV, HIV, and syphilis)	X											
Urine drug test	X	X										
Alcohol breath test	X	X										
COVID-19 precautions j	X	X										
Vital signs k		X b										
Clinical laboratory tests (hematology, clinical chemistry, and urinalysis)	X	X b						X				X

**Table 1-1: Schedule of study assessments**

Procedure	Screening Period	In-Clinic Period (BL) c	Treatment Periods 1 and 2 d									EOS/ET e
			In-Clinic Period c		Observation Period c							
Day a	-35 to -2	-1	1	2	3	5	8	15	22	29	35	
Throat swab for N. meningitidis	X											
12-lead ECG	X											
Recording of prior and concomitant medication and procedures	X	X b	X	X	X	X	X	X	X	X	X	
Recording of AEs	X	X b	X l	X l	X	X	X	X	X	X	X	X
N. meningitidis vaccination m	X	SoC	SoC	SoC	SoC	SoC	SoC	SoC	SoC	SoC	SoC	SoC
Randomization		X n										
IMP administration o			X									
Blood sampling for PK p			X	X	X	X	X	X	X	X	X	
Recording of device deficiencies and product quality complaints q			X									

AE=adverse event; BL=Baseline; COVID-19=coronavirus disease 2019; ECG=electrocardiogram; eCRF=electronic case report form; EOS=end of study; ET=early termination; FSH=follicle-stimulating hormone; HBsAg=hepatitis B surface antigen; HCV=hepatitis C virus; HIV=human immunodeficiency virus; IMP=investigational medicinal product; *N. meningitidis*=*Neisseria meningitidis*; PK=pharmacokinetic, SoC=standard of care

a Day -35 to -2 is relative to Day 1 in Treatment Period 1; all other days are relative to Day 1 within each Treatment Period.

b Baseline Day -1 procedures are repeated on Day -1 prior to Treatment Period 2, unless otherwise stated. Procedures to be repeated on the second Baseline Day -1 include vital signs, laboratory assessments, and recording of concomitant medications and AEs.

c Days -1, 1, and 2 are part of the In-Clinic Period; on Days 3, 5, 8, 15, 22, 29, and 35 of the Observation Period, participants will attend the study center to allow study assessments to be completed.

d Each participant will attend 2 Treatment Periods. There will 7 days of washout after completion of the first Treatment Period before returning to the study center for the second Treatment Period.

---

- c Study participants will have EOS procedures performed on the last sampling day (Day 35) of Treatment Period 2, in addition to the Day 35 procedures. Participants who prematurely withdraw from the study will return to the study center for the ET Visit as soon as possible after the time of withdrawal and will have all Day 35 (ie, Day 35 of the Treatment Period in which they withdrew from the study) and EOS procedures performed.
- f A full physical examination will be performed on all participants at Screening. On all other clinic visit days, the physical examination will be symptom directed.
- g For all women of childbearing potential, pregnancy testing will consist of a urine pregnancy test at the Screening and Baseline visits. Pregnancy test results must be negative prior to administering IMP. Positive urinary test will be exclusionary. Participant may rescreen at a later time if pregnancy not confirmed subsequently with a serum test.
- h Height will be measured only at the Screening Visit.
- i Only for postmenopausal women (for at least 1-year post-menopause before the Screening Visit) not using hormonal contraception or hormone replacement therapy.
- j COVID-19 precautions: latest procedure; site should follow local procedures/local policy for the management of COVID-19.
- k Systolic and diastolic blood pressure, pulse rate, and oral body temperature. Blood pressure and pulse measurements should be preceded by at least 5 minutes of rest for the participant.
- l If an injection site reaction is observed or reported by the participant, it should be recorded as an AE in the Case Report Form.
- m To reduce the risk of meningococcal infection (*N. meningitidis*), all study participants must be vaccinated against meningococcal infections (with a quadrivalent vaccine and serogroup B vaccine) within 3 years prior to, or at least 2 weeks prior to the start of initiating the IMP.
- n Treatment Period 1 only.
- o Study personnel will administer 1 injection to the study participant into the abdomen on Day 1 of each Treatment Period. The same dose of IMP will be administered for both Treatment Periods.
- p The PK sampling timepoints for each treatment period will be on Day 1 at predose and at 0.5h, 1h, 2h, 3h, 4h, 6h, 8h, and 12h and at 24h (Day2), 48h (Day 3), 96h (Day 5), 168h (Day 8), 336h (Day 15), 504h (Day 22), 672h (Day 29), and 816h (Day 35) postdose.
- q Device deficiencies will be reported via the eCRF. In addition, sites will fill out a product quality complaint form; all product quality complaints will be investigated by UCB.

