## 2.3 Benefit/risk assessment

This study will not provide a benefit to the study population, ie, healthy study participants.

The primary risk associated with C5 inhibitors as a class is increased susceptibility to infections with encapsulated bacteria, such as *Neisseria* spp. Specifically, this risk is related to suppression of the innate immune response and subsequent infections, particularly meningococcal infections. It is well established that inhibition of C5 and the terminal complement pathway increases the susceptibility to *Neisseria* spp. infections. Given the known increased risk of meningococcal infection (*Neisseria. meningitidis*) associated with inhibition or inherited deficiency of C5, participants in this study will be required to have documentation of *N. meningitidis* vaccination at least 2 weeks prior to IMP administration, if not vaccinated within 3 years prior to the start of treatment. Participants must be vaccinated with a quadrivalent vaccine (where available and in accordance with local standard of care) and serogroup B vaccine against meningococcal infections (*N. meningitidis*), and booster vaccinations should be administered in accordance with local standard of care. In addition, while on ZLP, study participants must be monitored closely for signs and symptoms of *N. meningitidis* infection, including self-monitoring on detailed instructions about signs and symptoms of possible meningococcal infections. To date, no meningococcal infections have been identified with ZLP treatment in clinical studies, as the risk of *Neisseria* infection is well-managed by appropriate prophylactic vaccination.

Considering the potential benefits, risks, and mitigation measures in place, UCB considers the overall benefit/risk to be favorable for participants in this study.

More detailed information about the known and expected benefits and risks and reasonably expected AEs of ZLP may be found in the ZLP IB and Zilbrysq summary of product characteristics (SmPC).

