##### **Type of participant and disease characteristics**

2. Participants who are overtly healthy as determined by medical evaluation including medical history, physical examination, laboratory tests, and cardiac monitoring.
3. Participants must be vaccinated with a quadrivalent vaccine and serogroup B vaccine against meningococcal infections (*N. meningitidis*) at least 2 weeks before the first administration of IMP if not previously vaccinated within 3 years prior to the start of IMP administration. Study participants who are not previously vaccinated may receive Menactra® (quadrivalent vaccine) and Bexsero® (serogroup B vaccine) during the Screening Period, 2 weeks prior to initiating IMP.

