### **6.5 Concomitant medication(s)/treatment(s)**

#### **6.5.1 Permitted concomitant treatments (medications and therapies)**

The following concomitant medications are permitted during the study:

- Paracetamol/acetaminophen for the treatment of mild symptoms (eg, headache or other pain), given at most every 6 to 8 hours, not exceeding 2g per day, and with a total of no more than 5g over 7 days.
- Ibuprofen, not exceeding 1.2g per day.
- Intranasal corticosteroids for seasonal rhinitis and topical corticosteroids for controlled dermatological conditions.

- Reliable contraceptives: Oral contraceptives not exceeding 30µg ethinyl estradiol or postmenopausal hormone replacement therapy or implants, patches, or intrauterine devices/intrauterine systems delivering progesterone (for female study participants).

The use of concomitant medications to treat AEs should be discussed between the Investigator and the Medical Monitor. All concomitant medications necessary for the health and well-being of a participant will be permitted.

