### **6.5.2 Prohibited concomitant treatments (medications and therapies)**

The following concomitant medications are prohibited during the study:

- Over-the-counter medications or prescription medications, vitamins, herbal/traditional medicines (including St John's Wort) or dietary supplements (excluding medicines for external use), with the exception of those specified in Section 6.5.1, within 2 weeks before the first administration of ZLP.
- Hepatic enzyme-inducing drugs (eg, glucocorticoids [except where permitted in Section 6.5.1], phenobarbital, isoniazid, phenytoin, rifampicin) should not be used within 2 months before the first administration of ZLP. In case of uncertainty, the Medical Monitor should be consulted.

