### **7.2 Participant discontinuation/withdrawal from the study**

Study participants are free to withdraw from the study at any time, without prejudice to their continued care.

A study participant may withdraw from the study at any time at their own request, or may be withdrawn at any time at the discretion of the Investigator for safety, behavioral, compliance, or administrative reasons.

If the study participant withdraws consent for disclosure of future information, the Sponsor may retain and continue to use any data collected before such a withdrawal of consent.

If a study participant withdraws from the study, they may request destruction of any samples taken and not tested, and the Investigator must document this in the site study records.

See the Schedule of Activities for data to be collected at the time of study withdrawal.

Study participants should be withdrawn from the study if any of the following events occur:

1. The study participant develops a clinically relevant medical condition (physical [eg, meningococcal disease] or psychiatric) that, in the opinion of the Investigator, jeopardizes or compromises the study participant's ability to participate in the study or makes it unsafe to continue.
2. Participant is noncompliant with the study procedures or medications in the opinion of the Investigator.
3. The study participant takes prohibited concomitant medications as defined in this protocol.
4. The study participant withdraws their consent.
5. The Sponsor or a regulatory agency requests withdrawal of the study participant.
6. The study participant has a confirmed positive serum pregnancy test.
7. The study participant has an anaphylactic reaction after their first injection.

Investigators should attempt to obtain information on study participants in the case of withdrawal.

Investigators should contact the UCB Medical Monitor, whenever possible, to discuss the withdrawal of a study participant in advance.

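### The vaccination rule states no minimum lead for a volunteer first vaccinated outside the study 1 to 13 days before the first injection

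*Protocol*

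**What the plan says.** The Protocol states the vaccination rule in three places.

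- **Section 1.3, Table 1-1, footnote m:** participants must have had the quadrivalent and serogroup B vaccines "within 3 years prior to, or at least 2 weeks prior to the start of initiating the IMP".
- **Section 5.1, criterion 3:** they must be vaccinated "at least 2 weeks before the first administration of IMP if not previously vaccinated within 3 years prior to the start of IMP administration". A second sentence lets people not previously vaccinated receive both vaccines "during the Screening Period, 2 weeks prior to initiating IMP".
- **Section 2.3:** documented vaccination is required "at least 2 weeks prior to IMP administration, if not vaccinated within 3 years prior to the start of treatment". Here the quadrivalent vaccine is qualified by local availability, and boosters follow local standard of care.

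The medication rules also bear on the point. Exclusion 5 and Section 6.5.2 bar over-the-counter and prescription medication; the wording in 6.5.2 is "with the exception of those specified in Section 6.5.1, within 2 weeks before the first administration of ZLP". Section 7.2 gives as a reason for withdrawal: "The study participant takes prohibited concomitant medications as defined in this protocol". The SAP sets no vaccination timing; its Section 6.7, on medications, only plans a listing of vaccinations.

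**The concern.** Section 2.3 names infection with encapsulated bacteria, meningococcal infection in particular, as the primary risk of C5 inhibitors, and says that these healthy participants get no benefit. For people it sends for vaccination, the protocol sets a 2-week lead before the first injection. It gives no reason why someone newly vaccinated elsewhere should need less.

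The wording nevertheless makes the 2-week lead an alternative to vaccination within 3 years (footnote m), or a condition that applies only when such vaccination is absent (criterion 3 and Section 2.3). A vaccination from last week is within 3 years, so the lead is never triggered. At stake is a safety interval for the main class risk. An investigator can still postpone Day 1, but the vaccination rule does not require it.

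**Working it through.** There is no figure in the plan to reproduce; the check is of the rule's logic.

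**Inputs.** Let t be the days from vaccination to first injection. Two weeks is 14 days and 3 years is 3 × 365 = 1,095 days. The Screening Period runs from Day -35 to Day -2 (Protocol Section 1.1) and there is no Day 0 (SAP Section 4.1.1.1), so a Screening Visit falls S = 2 to 35 days before Day 1.

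**Step 1: apply each version to a person whose only vaccination was t days ago.**

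| t (days) | Footnote m | Criterion 3 and Section 2.3 | Both limits required (14 ≤ t ≤ 1,095) |
|---|---|---|---|
| 1–13 | met (3-year limb) | met (2-week lead not triggered) | not met |
| 14–1,095 | met | met | met |

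Within 3 years, the written rule and a rule requiring both limits differ on exactly t = 1 to 13.

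**Step 2: who can have such a date?** A person vaccinated on or before the day of the Screening Visit has t ≥ S. The gap dates open to that person run from S to 13, which is 14 − S dates, or none if S ≥ 14.

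| S (assumed) | Gap dates |
|---|---|
| 2 | 12 |
| 7 | 7 |
| 13 | 1 |
| 14 to 35 | 0 |

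The documents do not say how S will be distributed. A person still unvaccinated at Screening is most naturally someone not previously vaccinated, and criterion 3 already sets the 2-week lead for that person.

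**Step 3: second injection.** Day 35 of Period 2 is Study Day 77 (Protocol Section 1.1) or 78 (SAP Section 1.2). Period 2 Day 1 is therefore Study Day 77 − 34 = 43 or 78 − 34 = 44, which is 42 or 43 days after the first injection. Even a vaccination given the day before the first injection is then 43 or 44 days old, so only the first injection is affected.

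**Step 4: length of a deferral.** A person vaccinated k days before the planned Day 1 (k = 1 to 13) would wait 14 − k days, that is 13 down to 1. The deferred Day 1 falls S + 14 − k days after Screening. For someone vaccinated on or before the Screening day, k ≥ S, so this is at most 14 days and fits the 35-day window. In general it fits if S ≤ 35 − (14 − k) = 21 + k, that is 22 to 34 days; beyond that the person is rescreened.

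**The case against.** **Previously vaccinated most naturally means before study entry.** Otherwise every vaccination given in Screening would also count as within 3 years, and the 2-week clause in criterion 3 would never operate. This stands. It confines the gap mainly to the group in Step 2 and leaves on-study vaccination outside it.

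**The medication ban covers the same 2 weeks.** A vaccine can be read as a prescription medication, and SAP Section 6.7 handles vaccinations alongside medications. This is a plausible barrier. A reader might infer that it fails outright, on two grounds, but the documents do not support going that far.

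- Section 6.5.1 ends with "All concomitant medications necessary for the health and well-being of a participant will be permitted". But the ban excepts what that section specifies, which is naturally its bulleted list. The closing sentence follows one about treating adverse events, and an elective vaccination is not plainly necessary in that sense.
- Table 1-1 marks standard-of-care meningococcal vaccination on Day -1, without the footnote saying "Procedures to be repeated on the second Baseline Day -1 include vital signs, laboratory assessments, and recording of concomitant medications and AEs". The entry is therefore not limited to Period 2. But the same mark runs through every column after Screening, which fits the boosters in Section 2.3. It does not show that first vaccination on Day -1 is intended.

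What remains is that the ban does not name vaccines. Whether it applies is left to the site to infer, although the protocol has a dedicated vaccination rule.

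**Other safeguards exist.** A positive throat swab or a history of meningitis excludes (exclusion 15), participants are closely monitored (Section 2.3), and they receive counselling and a safety card (Section 8.2.7). This lowers the stakes but sets no interval.

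**The wording may have changed.** The supplied protocol is the original of 11 Dec 2023; the SAP is based on Amendment 1 of 19 March 2024. This stands, and it decides the first step of the fix.

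**Conclusion.** The point holds as a minor patient-safety wording correction. None of the three statements sets a minimum lead for a volunteer first vaccinated outside the study 1 to 13 days before the first injection. The people concerned are mainly those vaccinated shortly before a Screening Visit less than 14 days before Day 1. Few or no participants are likely to be affected, and the bioequivalence analysis is unaffected.

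Two stronger readings are tempting. The first turns 13 of 1,095 dates (13/1,095 = 1.2%) into a chance that some of the 14 participants fall in the gap. That assumes that dates right up to the day before dosing are open to people who arrive already vaccinated. Step 2 shows that the number of available dates depends on S and is zero from S = 14 upward. Without S, and without the number arriving vaccinated, no probability follows. The second is that participants will be dosed without protection. The documents do not say how quickly protection develops, and the medication ban, the other safeguards or the investigator's judgement may prevent such a case.

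The conclusion rests on the original protocol text and assumes that Amendment 1 left it unchanged.

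**What to change.** First check Amendment 1. If the wording is unchanged, replace only the timing phrase in footnote m, criterion 3 and Section 2.3 with one common rule:

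> For each required vaccine, at least one qualifying vaccination must have been given no more than 3 years and no less than 2 weeks before the first IMP administration. A booster given in the last 2 weeks does not cancel an earlier qualifying vaccination. If no qualifying vaccination is yet 2 weeks old, Day 1 is deferred until one is.

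Leave the local-availability qualifier for the quadrivalent vaccine in Section 2.3 as it is. Check vaccination dates no later than the Day -1 eligibility review and before randomization, which is also on Day -1 of Period 1, so that nobody is randomized and then deferred.

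The cost is a wording amendment in three places and, for a rare volunteer, a deferral of 1 to 13 days or, where the Screening window would be exceeded, rescreening.
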